16.2.1.3 Non-parametric analysis of covariance

A non-parametric ANCOVA model (Koch 1998) will be used as sensitivity analysis for certain binary endpoints and also for continuous endpoints that risk having a large deviation from a normal distribution.

The macro NParCov3 will be used (Zink 2012). Input dataset to the macro should only contain the two treatments to be compared and only data from one visit.

The macro call will follow the below templates where covariates (in numeric format only) may be added or removed as required (max one strata variable can be specified).

For continuous variables

```
%nparcov3(outcomes=outcome, covars=cov1 cov2, c=1, hypoth=alt, strata=strata, trtgrps=treatment, transform=none, combine=first, dsnin=, dsnout=out);
```

Data sets “*_out_deptest*” and “*_out_ci*” will be automatically created by the macro and contains the following:

- “*_out_deptest*” provides estimate and p-value for the treatment difference, and
- “*_out_ci*” provides a 95% confidence interval for the treatment difference.

For binary variables

```
%nparcov3(outcomes=outcome, covars=cov1, c=1, hypoth=alt, strata=strata,  
trtgrps=treatment, transform=logistic, combine=first, dsnin=, dsnout=out);
```

The odds ratio and confidence interval can be obtained from “*_out_ratioci*”.

16.2.2 Analysis of binary and categorical data

16.2.2.1 Summary statistics for binary and categorical data

Summary statistics for discrete variables will be presented in contingency tables and will include count and frequency in each category. If applicable, confidence intervals will be derived as well based on the score method including continuity correction (Newcombe 1998):

With z as $(1-\alpha/2)$ -quantile of the standard normal distribution (SAS: $z=\text{probit}(1-\alpha/2)$, n as total number of subjects (i.e. number of subjects in the denominator), p as estimated crude incidence (number of subjects with event / n) and $q = 1-p$

Then the lower limit is

$$L = 100 \times \max \left(0, \frac{2np + z^2 - 1 - z\sqrt{z^2 + 2 - \frac{1}{n} + 4p(nq+1)}}{2(n+z^2)} \right)$$

and the upper limit is

$$U = 100 \times \min \left(1, \frac{2np + z^2 + 1 + z\sqrt{z^2 + 2 - \frac{1}{n} + 4p(nq-1)}}{2(n+z^2)} \right).$$

In addition, if $L > p$ then $L = p$ and if $U < p$ then $U = p$.

For binary response variables the placebo-adjusted response rates including 95% confidence interval will be derived.

SAS code for risk difference:

```
proc freq data=;
tables response*trt/ riskdiff;
run;
```

Note the response value should be sorted with ‘1’ ahead of ‘0’.

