In the responder analyses, treatment groups will be compared with respect to response to treatment using a logistic regression model with treatment and randomization stratum (region)

[figure not shown]
as factors, baseline SF-36 PCS score and baseline weight as covariates up to Week 16. Odds ratios and 95% CI will be presented for treatment comparison. Post Week 16, the proportion of responders will be descriptively summarized along with its 95% confidence intervals for each treatment sequence.

The SF-36 domain scores will be summarized.

12 [REDACTED] evaluations (change / add PD, [REDACTED]/PD,
Biomarkers, as needed)

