13.6 Compound specific safety evaluation

Safety topics of interest, such as risks defined in the Safety Profiling Plan (SPP), Risk Management Plan or topics of interest regarding signal detection or routine analysis are defined in the Program Case Retrieval Sheet that is stored in CREDI at the path Cabinets/CREDI Projects/A/AIN457A/Integrated Medical Safety.

The crude incidence and exposure-adjusted incidence rates for SPP risks will be summarized. In addition, listings will be provided presenting which subjects experienced which risk.

Important note: For the evaluation of SPP risks primary and secondary system organ classes of the MedDRA dictionary will be considered.

14 Interim analyses

The primary analysis will be performed after all subjects have completed the Week 16 visit in order to support regulatory filing. As the primary analysis is scheduled at Week 16, no adjustments will be made to the testing strategy to control the family-wise type I error. The investigators, site personnel and monitors will continue to remain blinded to the treatment each subject received at randomization all patients have completed the study (Week 60 Follow up) and the final database lock has occurred. Additional analyses may be performed to support interactions with health authorities, as necessary.

15 Determination of sample size

The sample size calculation is driven by the patient exposure requirements in the study population. An overall type I error (2-sided) 5% will be used to control type I error. Secukinumab 150 mg regimen will be tested versus placebo with respect to the primary endpoint (ASAS20 response at Week 16). A sample size of 300 patients in secukinumab 150 mg group and 150 patients in placebo group (randomization ratio = 2:1) is chosen in order to expose 300 patients to secukinumab for safety evaluation and also to achieve adequate power for the primary and secondary endpoints for this study.

Analysis of an unpublished phase III study showed a placebo response rate of about 28.4% and active drug response rate of 61.1% after 16 weeks for ASAS20. Using these assumptions, overall, the power for the ASAS20 endpoint should be about 99% with 300 patients in secukinumab 150 mg group and 150 patients in placebo group based on Fisher's exact test (nQuery Advisor 7.0).

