16.2.4 Crude incidence and related risk estimates

16.2.4.1 Crude incidence and 100*(1- α)% confidence interval

For n subjects, each at risk to experience a certain event with probability π , the crude incidence is estimated as $p=x/n$, where x is the number of subjects with the event.

Absolute and relative frequencies will be displayed as well as 95% confidence interval for the relative frequency based on the score method including continuity correction ([Newcombe 1998](#)).

With z as $(1-\alpha/2)$ -quantile of the standard normal distribution (SAS: $z=\text{PROBIT}(1-\alpha/2)$), n as total number of subjects (i.e. number of subjects in the denominator), and p as estimated crude incidence (number of subjects with event / n) it is $q=1-p$.

Then the lower limit is

$$L = \max\left(0, \frac{2np + z^2 - 1 - z\sqrt{z^2 + 2 - \frac{1}{n} + 4p(nq+1)}}{2(n+z^2)}\right)$$

and the upper limit is

$$U = \min\left(1, \frac{2np + z^2 + 1 + z\sqrt{z^2 + 2 - \frac{1}{n} + 4p(nq-1)}}{2(n+z^2)}\right).$$

In addition, if $L > p$ then $L = p$ and if $U < p$ then $U = p$.

If appropriate, an exact 100*(1- α)% confidence interval ([Clopper-Pearson 1934](#)) will be obtained by using the SAS procedure PROC FREQ with the EXACT BINOMIAL statement. However, the confidence interval derived via the score method including continuity correction will be the default in safety analyses.

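### SAP 16.2.2.1 caps score limits expressed in percent against p expressed as a proportion, so followed literally almost every lower limit is overwritten by p and the upper cap can never act (minor; descriptive intervals only)

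*SAP*

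**What the plan says.** SAP 16.2.2.1 covers summary statistics for binary and categorical data. Where intervals are wanted, it prescribes the score method with continuity correction and writes out the limits. It sets p as the "estimated crude incidence (number of subjects with event / n"), and q as 1 − p. Both limits carry a leading factor of 100: L is 100 times the larger of 0 and the lower root, and U is 100 times the smaller of 1 and the upper root. The closing rule is "In addition, if $L > p$ then $L = p$ and if $U < p$ then $U = p", with no factor of 100 on p.

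SAP 16.2.4.1 gives the corresponding interval for crude adverse event incidence: "Absolute and relative frequencies will be displayed as well as 95% confidence interval for the relative frequency based on the score method including continuity correction". The formula and closing rule are the same, but neither limit is multiplied by 100.

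SAP 11.7 contains a documented use of intervals for response proportions. For the SF-36 PCS and ASQoL responder analyses after Week 16, "the proportion of responders will be descriptively summarized along with its 95% confidence intervals for each treatment sequence". It does not say which interval formula is meant.

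**The concern.** L and U are percentages, p is a proportion, and the rule both compares them and substitutes one for the other. A rule meant to act only at the edge of the range would instead replace nearly every lower limit with a number below 1. The matching protection for the upper limit would be lost.

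The responder rates after Week 16 are reported by proportion and interval alone, with no model or test beside them. SAP Section 3 asks for tables for the Chinese population and overall, so the same fault would recur across outputs. The SAP is also the standard against which programs are checked: code that follows 16.2.2.1 gives wrong intervals, and code that gives right intervals departs from the text.

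**Working it through.** **Inputs.** Formula, p, q and cap: SAP 16.2.2.1. z = 1.96 (z² = 3.8415), the 0.975 normal quantile for a 95% interval. Group sizes and rates for the examples: SAP Section 15 ("A sample size of 300 patients in secukinumab 150 mg group and 150 patients in placebo group"; "active drug response rate of 61.1% after 16 weeks for ASAS20") and Table 15-1, rounded to whole counts (0.611 × 300 = 183.3, so 183; 0.284 × 150 = 42.6, so 43; and so on). Section 16.2.2.1 prints no worked interval to reproduce. As a check on the inputs, an exact Fisher enumeration at 61.1% versus 28.4% gives power 0.999999, in line with the stated figure of about 99%.

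**Formula as printed.**

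L = 100 × max(0, [2np + z² − 1 − z√(z² + 2 − 1/n + 4p(nq + 1))] / [2(n + z²)])

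U = 100 × min(1, [2np + z² + 1 + z√(z² + 2 − 1/n + 4p(nq − 1))] / [2(n + z²)])

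**One case in full: 183 of 300 (p = 0.61, q = 0.39).**

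- Lower: under the root, 5.8381 + 4 × 0.61 × 118 = 293.758; root 17.139; L = 100 × (366 + 3.841 − 1 − 33.593) / 607.683 = 55.17.
- Upper: under the root, 5.8381 + 4 × 0.61 × 116 = 288.878; root 16.996; U = 100 × (366 + 3.841 + 1 + 33.312) / 607.683 = 66.51.
- Cap as written: 55.17 > 0.61, so L becomes 0.61. 66.51 is not below 0.61, so U stays.

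**Other planning rates.**

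| Endpoint, arm | Count | Limits before cap (%) | After literal cap |
|---|---|---|---|
| ASAS20, secukinumab | 183/300 | 55.2 to 66.5 | 0.61 to 66.5 |
| ASAS20, placebo | 43/150 | 21.6 to 36.7 | 0.29 to 36.7 |
| ASAS40, secukinumab | 108/300 | 30.6 to 41.7 | 0.36 to 41.7 |
| ASAS 5/6, secukinumab | 129/300 | 37.3 to 48.8 | 0.43 to 48.8 |
| Partial remission, secukinumab | 42/300 | 10.3 to 18.6 | 0.14 to 18.6 |
| Partial remission, placebo | 6/150 | 1.4 to 8.9 | 0.04 to 8.9 |

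These rows show the size of the effect at the plan's own rates. They do not show that the SAP assigns this interval to each of these endpoints.

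**All possible counts.** Running x = 0 to n, the lower limit escapes only at x = 0, 1 and 2, where the formula truncates it to 0. It is overwritten for 298 of 301 counts at n = 300 and 148 of 151 at n = 150. Every other size tried (30, 60, 120, 240, 360, 450) shows the same pattern.

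**Upper cap.** At x = n = 300, p = 1 and q = 0. Under the root, 5.8381 − 4 = 1.8381; U = 100 × (600 + 3.841 + 1 + 2.657) / 607.683 = 99.97, below the observed 100%. At n = 150 it is 99.94. This is where the cap is needed, but 99.97 is not less than 1, so it does nothing.

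**Same rule on one scale, as in 16.2.4.1.** With the printed formula the lower cap never acts at n = 300 or 150, and the upper cap acts only at x = n.

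**Sign under the lower root.** Solving (p − 1/(2n) − L)² = z²L(1 − L)/n gives z² − 2 − 1/n + 4p(nq + 1) under the root, where both sections show + 2. With − 2, L for 183/300 is 55.21 instead of 55.17. The literal cap then overwrites all 301 and all 151 counts. On one scale the lower cap acts only at x = 0 (L = 0.03% at n = 300). The scale mismatch is there under either sign.

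**Could p be meant as a percentage?** No. With p = 61, q = 1 − p = −60, and the lower root would be taken of 5.84 + 4 × 61 × (300 × (−60) + 1), about −4.39 million.

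**The case against.** The strongest reply is that this is a slip of units and not a decision that could mislead. The method is named and referenced, and 16.2.4.1 prints the rule correctly, so the intent is not in doubt. An interval of 0.61 to 66.5 beside a rate of 61% would be seen in program validation. For arm-level response rates under multiple imputation, SAP 16.2.3.1 requests the continuity-corrected Wilson limits from a SAS option, with no hand-written cap. All of this stands and limits the weight of the point. It does not make the text right: the imputation code covers only those analyses, and 16.2.4.1 does not amend 16.2.2.1.

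A reader might infer more than the documents support, in three ways:

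- **That efficacy conclusions are at risk.** They are not. The primary and binary secondary endpoints are tested by logistic regression with odds ratios (SAP 11.4 and 11.5), and the placebo-adjusted response rate comes from a PROC FREQ risk difference.
- **That safety intervals are wrong.** SAP 13.1 sends crude incidences to 16.2.4.1, where the scales agree.
- **That 16.2.2.1 is the declared default for every response rate.** It is not. That section offers intervals only where applicable. The SAP calls the score interval a default in 16.2.4.1, for safety analyses. That the responder rates in 11.7 use 16.2.2.1 is a plausible inference, since 11.7 has no cross-reference.

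**Conclusion.** The rule is wrong as written, and the severity is minor. Taken literally with the printed formula, 16.2.2.1 replaces the lower limit by p for every count of 3 or more and disables the upper cap in the one case that needs it. The exact tallies of 298/301 and 148/151 depend on the printed sign under the lower root; the mismatch itself does not. The affected outputs are descriptive intervals for response proportions taken from this section, plausibly the SF-36 PCS and ASQoL responder rates after Week 16. Whether any table would actually be wrong depends on the macro, which the documents do not show.

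**What to change.** In 16.2.2.1, compute L and U on the proportion scale as 16.2.4.1 does, apply the cap there, and multiply by 100 only for display. Equivalently, keep the factor 100 and compare with, and replace by, 100p in both halves of the rule. Confirm that the macro does this, with x = 0, a mid-range count and x = n as test cases. When the line is edited, check the sign under the lower root in both sections against the cited source. A cross-reference from 11.7 to the intended interval would remove the remaining doubt about where it applies.

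The cost is one line of SAP wording and a short program check. No new data or analysis is needed.

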3.1 Study design

This multicenter study uses a randomized, double-blind, placebo-controlled, parallel-group design. A screening (SCR) period running up to 10 weeks before randomization will be used to assess eligibility, followed by 52 weeks of treatment.

[figure not shown]
At baseline, patients will be randomized to one of the two treatment groups:

- **Group 1: 300 patients**, secukinumab 150 mg (1 mL, 150 mg/mL) s.c. PFS at BSL, Weeks 1, 2, and 3, followed by administration every four weeks starting at Week 4
- **Group 2: 150 patients**, placebo (1 mL) s.c. PFS at BSL, Weeks 1, 2, 3, 4, 8, and 12, followed by secukinumab 150 mg (1 mL, 150 mg/mL) administration every four weeks starting at Week 16

The patients will be stratified at randomization according to the region (China and non-China). Approximately 80% of randomized patients will be from China (360 Chinese patients) in order to evaluate the efficacy and safety in this patient population. No more than 30% TNF α Inhibitor Incomplete Responders (TNF-IR) patients will be enrolled in the study.

Starting at Week 16, all patients will switch to open-label secukinumab 150 mg, including all placebo patients; however, all patients and investigators/site staff will remain blinded to the original randomized treatment group assignment (150 mg vs placebo). Study treatment will continue up to Week 48.

An end of treatment visit is to be done 4 weeks after last study treatment administration and a post treatment follow-up visit is to be done 12 weeks after last study treatment administration for all subjects (regardless of whether they complete the entire study as planned or discontinue prematurely).

Figure 3-1 **Study design**

Subjects will be instructed in detail how to self-administer the s.c. injection using PFS. Each injection will be administered into an appropriate injection site of the body (thighs, arms, or abdomen). All injections will be performed at the study site. Site personnel may administer the injections to subjects who are not able to, or feel insecure to self-administer (see [Section 5.5.4](#) for more details).

Rescue medication is not allowed until Week 20 (see [Section 5.5.6](#) for more details). However, subjects who are deemed by the investigator not to be benefiting from the study treatment based on safety and efficacy assessments or for any reason of their own accord will be free to discontinue participation in the study at any time.

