4.2 Treatment groups

The summaries by treatment will primarily be performed by the randomized treatment but also by combination of randomized treatment and switch treatment. For some safety summaries (e.g. exposure-adjusted) the ‘switch’ treatment may be summarized separately.

- Randomized treatment:
 - AIN457 150 mg
 - Placebo
- Treatment sequence:
 - AIN457 150 mg
 - Placebo – AIN457 150 mg
- Switch treatments (for patients who cross-over):
 - AIN457 150 mg

5 Subgroup definitions

The primary and secondary endpoints will be analyzed by region (China and non-China). Analyses by previous use of TNF- α inhibitor will also be provided for total population and Chinese population.

6 Assessment windows, baseline and post baseline definitions, missing data handling

Baseline and post-baseline definitions

In general, a *baseline* value refers to the last measurement made prior to administration of the first dose of study treatment. A post-baseline value refers to a measurement taken after the first dose of study treatment.

Analysis visit windows

Analysis visit windows will be used for the data that is summarized by visit; they are based on the study evaluation schedule and comprise a set of days around the nominal visit day. For any assessment, there are protocol defined scheduled visits around which analysis visit windows were created to cover the complete range of days within the study. The analysis visit windows and rules for dealing with multiple measurements within the windows are described in [Appendix 16.1](#).

7 Subject disposition, background and demographic characteristics

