11.4 Analysis of primary variable

The primary efficacy variable is response to treatment according to the ASAS20 criteria at Week 16. The analysis of the primary variable will be based on the FAS patients.

Description

The ASAS Response Criteria (ASAS20) is defined as an improvement of $\geq 20\%$ and ≥ 1 unit on a scale of 10 in at least three of the four main domains and no worsening of $\geq 20\%$ and ≥ 1 unit on a scale of 10 in the remaining domain.

Statistical analyses

The statistical hypothesis for ASAS20 being tested is that there is no difference in the proportion of subjects fulfilling the ASAS20 criteria at Week 16 in secukinumab regimen versus placebo regimen.

Let p_0 denote the proportion of ASAS20 responders at Week 16 for Placebo regimen and p_1 denote the proportion of ASAS20 responders at Week 16 for Secukinumab 150 mg regimen,

In statistical terms, $H_0: p_1 = p_0$, $H_{A1}: p_1 \neq p_0$, i.e.

H_1 : Secukinumab 150 mg regimen is not different to placebo regimen with respect to ASAS20 response at Week 16

The primary analysis will be conducted via logistic regression with treatment, randomization stratum (region) as factors and baseline weight as a covariate. Odds ratios and 95% CI will be presented comparing secukinumab 150 mg regimen to placebo.

Supportive analyses

Sensitivity analyses and supportive analyses will be conducted in order to provide evidence that the results seen from the primary analysis are robust.

In order to determine the robustness of the logistic regression model used for the primary analysis, ASAS20 response at Week 16 will also be evaluated using a non-parametric

ANCOVA model ([Koch 1998](#)) with the same independent variables as the logistic regression model.

Interactions between treatment and selected baseline demographics and disease characteristics will be explored.

The impact of missing data on the analysis results of ASAS20 response will be assessed as well by repeating the logistic regression model using different ways to handle missing data. These may include, but are not limited to:

- Multiple imputation
- Observed data analysis

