16.2.4.3 Risk difference and 100*(1- α)% confidence interval

For an investigational drug group with n_1 subjects at risk, independent from the control group (e.g. placebo or comparator) with n_0 subjects at risk, of whom x_1 and x_0 experience a certain event, the risk difference is estimated as p_1-p_0 with $p_1=x_1/n_1$ and $p_0=x_0/n_0$.

Exact unconditional confidence limits for the risk difference can be obtained with SAS procedure PROC FREQ and option RISKDIFF in the TABLES statement, specifying the RISKDIFF option also in the EXACT statement.

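### The difference in response rates for binary efficacy endpoints omits the region stratum and uses default large-sample limits: sound overall, weak in small subgroups with few placebo responders

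*SAP*

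**What the plan says.** - **The estimate.** SAP 16.2.2.1: "For binary response variables the placebo-adjusted response rates including 95% confidence interval will be derived". The code is "tables response*trt/ riskdiff", with no stratum variable, no option for the interval method and no EXACT statement. For single proportions the same section specifies a continuity-corrected score interval.
- **The other risk difference.** SAP 16.2.4.3, under crude incidence and related risk estimates: "Exact unconditional confidence limits for the risk difference can be obtained with SAS procedure PROC FREQ and option RISKDIFF in the TABLES statement", with the option repeated in an EXACT statement. So the SAP distinguishes limits that have to be requested from those that come by default.
- **The design and the models.** Protocol 3.1 stratifies randomisation by region (China, non-China). SAP 11.4: "The primary analysis will be conducted via logistic regression with treatment, randomization stratum (region) as factors and baseline weight as a covariate". SAP 11.5 uses the same model for ASAS40, ASAS 5/6 and partial remission. These models report odds ratios, and so does the non-parametric ANCOVA for binary endpoints (SAP 16.2.1.3).
- **The tables.** SAP section 3 produces tables for the Chinese population and overall. SAP section 5 analyses the primary and secondary endpoints by region, and by prior TNF inhibitor use in the total and Chinese populations. It does not say whether the rate difference will be shown in each subgroup.

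**The concern.** The odds ratio and the rate difference for one endpoint would rest on different analyses: one adjusted for region and weight, the other for neither. The rate difference is the figure clinicians and assessors read most easily, and for binary efficacy the SAP offers no other absolute contrast between arms.

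The simple large-sample interval uses each arm's observed variance. An arm with zero responders has an estimated variance of zero, so the interval treats that arm's rate as known. Partial remission has a planning rate of 4.1% on placebo, so this can easily happen in a small subgroup. SAP 16.2.2.2 foresees 0% or 100% response and gives the odds ratio a fallback (exact logistic regression, then Fisher's test). The rate difference has none.

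**Working it through.** **Inputs.** 300 versus 150 patients, 2:1, two-sided 5% (SAP 15). Rates, secukinumab versus placebo (SAP 15.1): ASAS20 61.1/28.4%, ASAS40 36.1/10.8%, ASAS 5/6 43.1/8.1%, partial remission 13.9/4.1%. About 360 of 450 patients from China (Protocol 3.1), hence about 240/120 in China and 60/30 outside. At most 30% TNF-inhibitor incomplete responders (TNF-IR): 0.30 × 450 = 135, or 90/45. Non-responder imputation keeps dropouts in the denominators.

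**Assumptions.** Plain RISKDIFF gives the Wald interval. The table has treatment as rows. The overall planning rates apply in each subgroup.

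**1. The plan's own figures.** The documents state power but no interval width or coverage. Fisher power by full enumeration is above 99.9% for ASAS20 (stated: about 99%) and 93.1% for partial remission (stated: 92%). The inputs are therefore read correctly.

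**2. Overall ASAS20, effect of stratifying.** The unstratified variance is 0.611×0.389/300 + 0.284×0.716/150 = 0.002148, so the half-width is 1.96 × 0.04635 = 9.08 points. The stratified variance is 0.8² × (China variance at 240/120) + 0.2² × (non-China variance at 60/30). The documents give no rates by region, so I assume a gap g in both arms and hold the overall rates fixed: China p + 0.2g, non-China p − 0.8g.

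| Assumed gap (points) | Stratified half-width (points) | Narrowing |
|---|---|---|
| 0 | 9.08 | 0% |
| 10 | 9.05 | 0.4% |
| 20 | 8.95 | 1.5% |
| 30 | 8.77 | 3.4% |

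**3. Coverage, enumerating both binomials.** Ranges are over the four binary endpoints.

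| Table | Wald coverage |
|---|---|
| Overall, 300/150 | 94.8-94.9% |
| China, 240/120 | 94.7-95.0% |
| TNF-IR at the cap, 90/45 | 94.4-94.5% |
| Non-China, 60/30 | 93.9-94.3% |

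At 60/30 the Wald lower limit exceeds the true difference 3.7-4.1% of the time (nominal 2.5%). With Miettinen-Nurminen limits this falls to 1.0-2.5%. Score-type coverage at 60/30 is 94.5-97.1%.

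**4. Zero placebo responders, partial remission.** Non-China: (1 − 0.041)^30 = 0.285. TNF-IR at the cap: (1 − 0.041)^45 = 0.152. Chinese table: (1 − 0.041)^120 = 0.007.

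An example at 60/30 is 8/60 versus 0/30, a difference of 13.3 points:
- Wald: standard error √(0.1333×0.8667/60 + 0) = 0.0439, interval 4.7 to 21.9 points.
- Newcombe: interval 0.3 to 24.2 points. Here the Wilson upper limit for 0/30, 3.84/(30 + 3.84) = 11.4%, enters the lower bound.

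With 7/60 versus 0/30, Wald starts at +3.5 points and Newcombe at −1.1.

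**The case against.** The case for leaving the text alone is substantial.

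- **The overall interval is sound.** A crude difference after stratified randomisation is valid and at worst slightly conservative. A reader might infer that the overall intervals are too wide. That holds only if region predicts response, which the documents do not show. This stands.
- **The subgroup intervals are not simply wrong.** At the planning rates the shortfall at 60/30 is about one point or less. The 4.7 to 21.9 interval above still contains the planning difference of 13.9 − 4.1 = 9.8 points. This stands for average coverage. The excess does fall on the favourable side, and Wald coverage given zero placebo remissions at 60/30 is 87.1%.
- **Score limits have their own error.** For non-China partial remission Newcombe covers 97.1% against 94.1% for Wald, so it is further from 95%, and part of the gap between the two intervals is its caution. This stands as a cost.
- **The China submission is not where the weakness lies.** A reader might infer that the submission tables are compromised. SAP section 3 ties the submission to the Chinese and overall tables, where coverage is 94.7-95.0%. The clearest problem is in the non-China table. This stands.
- **It is a summary statistic.** It enters none of the hypotheses H1 to H8, and separation is handled for the odds ratio. This stands, and limits the matter to reporting.

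A reader might also take this for the SAP's only absolute effect. It is not: 16.2.4.3 gives a risk difference for crude incidences, and the repeated-measures models give mean differences. It is the only one for binary efficacy.

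**Conclusion.** The point holds as a minor reporting improvement. The between-arm rate difference for binary efficacy is unstratified and uses default limits, in contrast to the region-adjusted odds ratios beside it.

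Overall the argument is mainly consistency, since the gain in width is 0-3.4% and nil if region is not prognostic. In small subgroups there is mild, one-sided undercoverage and a specific failure when the placebo arm has no responders. The subgroup part is conditional: SAP section 5 does not say that this template will be used there, although it is the only one given for binary efficacy differences. Omitting region has no effect within a single-region table, so only the choice of limits matters there.

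The figures rest on the planning rates applying in each subgroup, the 80:20 regional split, 2:1 allocation within subgroups, and TNF-IR enrolment at the 30% cap.

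**What to change.** Amend SAP 16.2.2.1 before unblinding:

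- **Overall tables:** report the region-stratified (Mantel-Haenszel weighted) risk difference with a stratified score-type interval.
- **Single-region tables (China, non-China):** use Miettinen-Nurminen or Newcombe score limits.
- **Prior-TNF tables:** use score limits, stratified by region in the total population.
- State whether the rate difference is shown in the section 5 subgroups.

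Correct a separate fault on the same code line at the same time. The table is written response by treatment, so the row comparison contrasts treatment shares among responders and non-responders. The Fisher code in 16.2.2.2 has treatment first.

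The cost is about one sentence and one code line. Score limits will be somewhat conservative, and wider for rare responses in small subgroups. For common responses they need not be wider: the mean ASAS20 width at 60/30 is 38.6 points for Newcombe against 40.0 for Wald. The odds ratios, primary test and testing sequence stay as planned.

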15.1 Power for analysis of secondary variables

A summary of the assumptions and power for the primary and secondary efficacy parameters using the same unpublished study is shown in [Table 15-1](#) for binary endpoints and [Table 15-2](#) for continuous endpoints.

Table 15-1 Summary of power for binary endpoints

Endpoint	Response Rate		Power
	Secukinumab 150 mg (N=300)	Placebo (N=150)	
ASAS20	61.1%	28.4%	99%
ASAS40	36.1%	10.8%	99%
ASAS5/6	43.1%	8.1%	99%
ASAS partial remission	13.9%	4.1%	92%

Table 15-2 Summary of power for continuous endpoints

Endpoint	Mean change from baseline		Common standard deviation	Power
	Secukinumab 150 mg (N=300)	Placebo (N=150)		
hsCRP	-0.60	0.12	0.84	99%
Total BASDAI	-2.19	-0.85	2.10	99%

Endpoint	Mean change from baseline		Common standard deviation	Power
	Secukinumab 150 mg (N=300)	Placebo (N=150)		
SF-36 PCS	6.06	1.92	6.65	99%
ASQoL	-4.00	-1.37	4.45	99%

16 Appendix

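### The SAP's SAS line for the placebo-adjusted response rate has its two variables transposed, so the descriptive difference and its 95% CI do not estimate the difference in response rates

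*SAP*

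**What the plan says.** The prose of SAP 16.2.2.1 states the target plainly: "For binary response variables the placebo-adjusted response rates including 95% confidence interval will be derived". The code printed under it is "tables response*trt/ riskdiff". A note after the code says "Note the response value should be sorted with" level 1 ahead of level 0. No order is given for treatment.

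Two other places in the SAP bear on the orientation. In 16.2.2.2 the template for Fisher's exact test names treatment first and response second. In 16.2.4.3 "the risk difference is estimated as" p1 − p0, where p1 = x1/n1 and p0 = x0/n0, so the denominators are the patients at risk in each arm. Neither place amends the line in 16.2.2.1.

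For the primary endpoint, SAP 11.4 specifies logistic regression and states "Odds ratios and 95% CI will be presented comparing secukinumab 150 mg regimen to placebo". SAP 11.5 does the same for ASAS40, ASAS 5/6 and ASAS partial remission. Sections 11.4 and 11.5 name no absolute difference for these endpoints; that comes in only through the general sentence in 16.2.2.1.

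**The concern.** In a PROC FREQ two-way request the first variable forms the rows and the second the columns. RISKDIFF takes the proportion in a given column within each row and subtracts row 2 from row 1. With response in the rows and secukinumab in column 1, the output is P(secukinumab | responder) − P(secukinumab | non-responder). The denominators are the numbers of responders and non-responders, not the arm sizes, so the result depends on the randomization ratio as well as on the two response rates.

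The sorting note does not repair this. With response in the rows, it fixes only which response level is row 1. The note is what one would write for a table with response in the columns, which suggests that the two variables were swapped by mistake.

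At stake is the absolute treatment difference for the binary endpoints, which a reader would set beside the odds ratio. The Week 16 analysis is meant to support regulatory filing (SAP 14), and tables are produced for the Chinese population and overall separately (SAP 3). An uncorrected template could carry the error into several sets of output.

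**Working it through.** **Inputs.** Arm sizes are 300 secukinumab and 150 placebo (SAP 15). Planning response rates are from SAP Table 15-1, "Summary of power for binary endpoints": ASAS20 61.1% v 28.4%, ASAS40 36.1% v 10.8%, ASAS 5/6 43.1% v 8.1%, partial remission 13.9% v 4.1%.

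**The plan's own figures.** The documents give no figure for the risk difference, so the stated power was reproduced to confirm the inputs. Exact enumeration of the two-sided 5% Fisher test gives more than 99.9% for ASAS20 (stated: about 99%) and 93.1% for partial remission (stated: 92%). The inputs are read correctly.

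**What the printed line returns.** Let a and b be the expected responders on secukinumab and placebo. With secukinumab as column 1:

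template difference = a/(a+b) − (300−a)/(450−a−b)

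correct difference = a/300 − b/150

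- ASAS20: a = 0.611×300 = 183.3, b = 0.284×150 = 42.6. Template 183.3/225.9 − 116.7/224.1 = 0.8114 − 0.5207 = 0.291. Correct 0.611 − 0.284 = 0.327.
- ASAS40: a = 108.3, b = 16.2. Template 108.3/124.5 − 191.7/325.5 = 0.8699 − 0.5889 = 0.281. Correct 0.253.
- ASAS 5/6: a = 129.3, b = 12.15. Template 129.3/141.45 − 170.7/308.55 = 0.9141 − 0.5532 = 0.361. Correct 0.350.
- Partial remission: a = 41.7, b = 6.15. Template 41.7/47.85 − 258.3/402.15 = 0.8715 − 0.6423 = 0.229. Correct 0.098.

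**Intervals.** The line requests no special interval, so Wald limits are assumed: d ± 1.96·√[r1(1−r1)/n1 + r2(1−r2)/n2], where r1 and r2 are the two row proportions and n1 and n2 the row totals. For partial remission as printed, the standard error is √(0.8715×0.1285/47.85 + 0.6423×0.3577/402.15) = 0.054, giving 12.3 to 33.5 points. With treatment in the rows it is √(0.139×0.861/300 + 0.041×0.959/150) = 0.0257, giving 4.8 to 14.8.

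| Endpoint | As printed, points (95% CI) | Correct, points (95% CI) | Error |
|---|---|---|---|
| ASAS20 | 29.1 (20.8 to 37.4) | 32.7 (23.6 to 41.8) | −3.6 |
| ASAS40 | 28.1 (20.1 to 36.1) | 25.3 (17.9 to 32.7) | +2.8 |
| ASAS 5/6 | 36.1 (28.9 to 43.3) | 35.0 (27.9 to 42.1) | +1.1 |
| Partial remission | 22.9 (12.3 to 33.5) | 9.8 (4.8 to 14.8) | +13.1 |

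**Dependence on allocation.** This check illustrates the mechanism; the trial does not use 1:1 allocation. With the same rates at 225 per arm, the printed line gives 33.1, 35.2, 45.9 and 29.9 points, while the correct differences do not move.

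**Sign.** If placebo sorts into column 1, the column-1 difference has the same size and the opposite sign.

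**The case against.** The strongest reply is that this is a slip in an appendix template. The prose names the right quantity, 16.2.4.3 defines the risk difference with arm sizes as denominators, and the Fisher template in 16.2.2.2 has the usual orientation. A competent programmer would probably notice. No test, type I error control, power figure or odds ratio depends on the line, and a Fisher p-value is the same under either orientation. All of that stands, and it limits the consequences. It does not make the printed line correct, and a programmer who departs from the template is no longer following the SAP's code.

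The errors for ASAS20, ASAS40 and ASAS 5/6 are also modest, each printed value lying inside the correct 95% interval. With arm rates tabulated alongside, simple subtraction would expose them. The partial remission value exceeds the 13.9% active-arm rate, which a placebo-adjusted rate cannot do. This also stands: partial remission is the one materially distorted case, and it could be caught. But the error runs in both directions across endpoints, so no uniform correction is available to a reader.

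On sign, RISKDIFF by default prints differences for both columns, so the secukinumab column is available under either coding. The sign remark therefore holds only for the column-1 difference. Leaving the treatment order unstated still leaves open which column is to be read.

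Finally, 16.2.4.3 is permissive about exact limits and belongs to the section on incidence and risk estimates, so it does not contradict the default limits in 16.2.2.1. That is fair; naming the interval method is an optional clarification.

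**Conclusion.** The concern holds: the code line is wrong for its stated purpose. Run as printed, it would misstate the placebo-adjusted rate by −3.6, +2.8, +1.1 and +13.1 percentage points for ASAS20, ASAS40, ASAS 5/6 and partial remission. For partial remission the estimate is more than doubled and the interval excludes the correct 9.8 points. The consequence is confined to descriptive estimates and their intervals; confirmatory inference is unaffected.

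The sizes assume the planning rates, 300 and 150 patients, secukinumab as column 1 and Wald limits. Observed rates will change the sizes. The mismatch itself does not rest on the planning rates, but on how PROC FREQ arranges rows and columns, which is standard software behaviour and is not stated in the documents.

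**What to change.** In SAP 16.2.2.1, replace the line with `tables trt*response / riskdiff;`. State both orders explicitly (secukinumab as row 1, response = 1 as column 1) and specify that the column-1 risk difference is reported. The point estimate then equals p1 − p0 as defined in 16.2.4.3.

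Optionally, add one sentence naming the interval method. The corrected line gives asymptotic limits by default, whereas 16.2.4.3 notes that "Exact unconditional confidence limits for the risk difference can be obtained with SAS procedure PROC FREQ" with a further EXACT specification.

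The cost is one line of code and, at most, a few sentences. No test, endpoint, sample size or step in the hierarchy changes.
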